## 2.4 Data Acquisition

*Fill in all relevant information:*

Study design	Factorial trial
Data source/how the data were collected	Primary data collection from participants in North Carolina
Contact information for team member responsible for data collection/acquisition	[name] [contact]
Date or version (if downloaded, provide date)	October 21, 2019
Data transfer method and date	Transferred from Box to CRU drive on November 11, 2019
Where dataset is stored	A shared Box folder called "Charge Data Cleaning"

### 3 Outcomes, Exposures, and Additional Variables of Interest

#### 3.1 Primary Outcome(s)

- The primary outcome is absolute change in weight from baseline to 6 months. Weight is measured in duplicate by trained, certified staff.

#### 3.2 Secondary Outcome(s)

- Absolute change in weight from baseline to 12 months.

#### 3.3 Other variables of interest.

- Absolute change in weight from baseline to 3 months. Will be included for statistical modeling purposes.
- Engagement:

#### 3.4 Primary predictors

The primary predictors are the five text messaging intervention components listed in the table below. Detailed descriptions of these components are provided in Appendix A.

Intervention component	Default Level	Comparator Level
Motivational Messages	Expert generated	Self-generated
Texting frequency	Weekly	Daily
Reminders	One	Multiple
Feedback	Individual goal	Summary Score
Performance comparison	Self	Others (group)

## 4 Statistical Analysis Plan

**Notes:** *Participants in the full-length pilot will be included in the main analysis, since they ended up being recruited right about when the full trial started, and were not actually used to fix bugs in the program. In the primary analysis, those whose data is collected outside of the study window will be treated as missing for that time point. Sensitivity analyses will be performed including such data.*

For each of the five components, participants' weights and demographics will be summarized by levels of the component. Continuous variables will be summarized using means, standard deviations, medians, quartiles, and ranges, and categorical variables will be summarized using counts and percentages.

The primary outcome is absolute change in weight from baseline to 6 months. We will estimate the main effects of each intervention component on the primary outcome and of all pairwise interactions of those components at each follow-up time point using a linear mixed effects model. In order to estimate effects on weight change, the model will include as outcomes absolute weight at baseline and each follow-up time point. The model will include fixed effects for: time point (3 months, and 6 months, and 12 months), the time-by-component and time-by-pairwise up to five-way interactions, and gender (the variable by which the randomization was stratified). We do not include the effects of the components at baseline. This constrains the baseline comparisons to be equal, which is appropriate in a randomized trial and increases power. The model will allow us to estimate weight change and percentage weight change at the interim time point (month 3) and final follow-up time point (month 12), but the main estimate of interest will be the five treatment indicators by month 6 interaction.

After examining the model, we will assemble a multicomponent intervention package. If a component has a main effect on weight loss at 6 months greater than or equal to 0.7 kg (1.5 lbs), and no significant interaction with another component, then the superior level of the component will be retained for the intervention package. Otherwise, if there is no significant main effect or interaction, the default (reference) level of the component will be retained. We will reconsider inclusions based on the presence of large (effect  $\geq 0.7$  kg) interactions. This decision making is based on the approach outlined in Collins et al. Although the secondary outcome of 12-month weight will not be used in the *primary* decision-making process, we may reconsider our inclusions if there is a large change in effect between 6 months and 12 months.

Given the factorial design, we will use effect coding, rather than dummy coding, for analyzing the effects of the intervention components. If the sample size is equal per condition, all of the tests of main effects and interactions are uncorrelated—that is, the main effect of a condition is the same even if other treatment conditions and interactions are included in the statistical model. Even with unequal sample sizes across conditions (as may occur with differential dropout by condition), if the imbalance is minor, the correlations between effects should be small.

Missing outcome data due to dropout or missing intermediate visits is expected to be at most 30%. Since the mixed model will be fit using a full maximum likelihood method, we will be able to account for predictors of missingness in the model in order to obtain valid estimates of the main component effects, thanks to the property that the response can be missing at random (MAR) as defined by Little and Rubin. In practice, we will compare baseline characteristics of completers and non-completers. If we find that any covariates predict missingness, we will adjust for these variables in the model in order to obtain valid estimates.

In addition, we will examine gender as a potential moderator, where those who answered “non-binary” will be excluded from the analysis, given the extremely small numbers of participants who

answered this way. We acknowledge that we are not powered to detect moderators, but these results may be used to guide future studies.

Engagement data will be summarized and displayed in a table.

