***NCT03254940***

***Document date: January 21, 2021***

## ***STUDY PROTOCOL***

## Charge Full Research Protocol

*Optimal iOTA (Charge): Optimizing a standalone text messaging-based weight loss intervention*

**Overall study aim:** This will be a 12-month experimental trial among 448 adults with obesity to determine which stand-alone text messaging intervention components produce a meaningful contribution to 6-month weight change. We operationalize meaningful text messaging components as those having an effect size of  $> .15$ , using the Pellegrini et al. definition. We will use the multiphase optimization strategy (MOST) to help us assemble multicomponent interventions comprised only of components that meaningfully affect our chosen outcomes.

All participants will receive a core 6-month weight loss texting intervention (based on our iOTA approach) that includes tailored behavior change goals, interactive self-monitoring, automated feedback, and skills training. We will use a full factorial design to randomize participants to experimental conditions that reflect the texting intervention components: motivational messaging (self- vs expert-generated), texting frequency (daily vs weekly), reminders (one reminder v. multiple reminders), feedback type (summary score v. specific feedback) and comparison unit (to self v. to a group of people). The full factorial design is power efficient, logistically feasible (because we manipulate conditions using technology) and will allow us to examine the most important main and interaction effects among components.

Our primary outcome will be absolute change in weight from baseline to 6 months. We will estimate the main effects and 10 pairwise interactions of each of the five components on the outcome at each follow-up time point using a linear mixed effects model. The model will include fixed effects for: time point (baseline, 3- or 6-months), component (motivational messaging, frequency, reminders, feedback type, and comparison unit), pairwise interactions of each component and the time-by-component and time-by-pairwise interactions.

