a The primary measure is self-monitoring episodes (texts received/requests successfully sent). We will also examine skills training video views (completed views/video links successfully sent) and changes in motivational message content (content changes/change requests successfully sent).

b Defined as those who cease intervention participation, but do not drop out of the trial (i.e., they complete 6-month assessments). For each, we will define the week of nonuse as the week in which all intervention participation ceased, and the participant did not return to the intervention.

Baseline Enrollment Survey: Participants who express interest in Charge will be asked to take a series of Qualtrics surveys before coming in for a baseline visit. First, participants will take a short eligibility screener. Eligible participants will go through the informed consent process via Qualtrics and to sign an electronic informed consent form. Participants who sign the informed consent will be asked to fill out baseline surveys and the iOTA goal assignment survey. This survey was tested prior to implementation via mTurk to ensure they are not burdensome (pilot testing was approved in previous amendments).

Baseline Evaluation Visit: At the baseline evaluation visit, study staff will collect written informed consent, administer the motivational message survey (if applicable based on condition), and confirm participant eligibility. This will be followed by an individual orientation to the intervention. Participants will be reimbursed for their time at baseline visits.

We will randomize participants at the baseline visit. Randomization sequences will be generated by a computer algorithm using a covariate adaptive randomization method, in which group assignment will be informed by the balance of race/ethnicity and gender in the previously assigned participants. This method minimizes imbalance between groups for these characteristics, even in a small sample where the risk of imbalance is high and when the exact composition of the sample is not known a priori. Due to the nature of the interventions, it will be difficult to completely blind staff collecting data to treatment assignment. However, we will ensure that different study staff collect follow-up data and we will take all possible steps to blind those data collection staff to treatment assignment. Outcomes will be analyzed blind to allocation status.

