We will randomize participants at the baseline visit. Randomization sequences will be generated by a computer algorithm using a covariate adaptive randomization method, in which group assignment will be informed by the balance of race/ethnicity and gender in the previously assigned participants. This method minimizes imbalance between groups for these characteristics, even in a small sample where the risk of imbalance is high and when the exact composition of the sample is not known a priori. Due to the nature of the interventions, it will be difficult to completely blind staff collecting data to treatment assignment. However, we will ensure that different study staff collect follow-up data and we will take all possible steps to blind those data collection staff to treatment assignment. Outcomes will be analyzed blind to allocation status.

**Retention:** Our team has an excellent record of retaining our trial participants. In Shape, we retained 96% of participants (in a profoundly socioeconomically disadvantaged population) at the 18-month follow-up. In our current study, Track, we also have a >90% 6-month retention rate in a medically vulnerable population. We will use strategies that have been successful in prior studies (e.g., contacting through multiple channels, incentivizing provision of changed contact information, birthday/holiday cards, using family contacts, text messaging and social media). To maximize retention, participants will receive reimbursements at each of the evaluation visits: baseline, 3, 6, and 12 months. Participants who come to all 3 follow-up visits (after baseline) will receive another \$15. Home visits will be used when other contact strategies are exhausted. Despite our experience with participant retention, we have set a conservative floor of 70% retention at 6 months. We have exceeded this rate in all of our recent trials.

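### The protocol balances allocation on race/ethnicity and gender, but the SAP's primary model has gender only, with no visit interaction, so neither factor adjusts weight change

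*Combined protocol and SAP*

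**What the plan says.** **Protocol.** The Baseline Evaluation Visit text and the paragraph on screening, randomization and blinding (section 2) agree on the method: "Randomization sequences will be generated by a computer algorithm using a covariate adaptive randomization method". Both places then name the two factors that steer it: "group assignment will be informed by the balance of race/ethnicity and gender in the previously assigned participants". The opening summary of the protocol gives a model with neither factor: "The model will include fixed effects for: time point (baseline, 3- or 6-months), component", followed by the component interactions and their interactions with time.

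**SAP section 4.** The model is longitudinal: "the model will include as outcomes absolute weight at baseline and each follow-up time point". The fixed effects are time point, "the time-by-component and time-by-pairwise up to five-way interactions", and then "and gender (the variable by which the randomization was stratified". Baseline is constrained: "We do not include the effects of the components at baseline". The estimates of interest are the five component-by-month-6 terms. Race/ethnicity is not listed. It could enter only by the missing-data route: "If we find that any covariates predict missingness, we will adjust for these variables in the model". Gender as a moderator of component effects is a separate exploratory analysis.

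**The concern.** There are two linked problems.

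First, the documents disagree on what the allocation balanced. The protocol names two factors and a covariate-adaptive method. The SAP names one factor and calls it stratification.

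Second, the form of the gender term matters because the outcome vector is weight, not change. A lone gender term adds the same number of kilograms to a participant's expected weight at baseline, 3, 6 and 12 months, and so fixes the gender difference in change at zero. Any real difference in 6-month change by gender stays in the residual, and so does any difference by race/ethnicity.

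When allocation has balanced a prognostic factor, the component estimates vary less from trial to trial than a model without that factor believes. The reported standard errors are then too large. SAP section 4 uses significance of main effects and interactions, alongside the 0.7 kg threshold, to decide which component levels enter the package. Tests that are too conservative push that choice towards the default levels and can hide interactions.

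**Working it through.** **Inputs from SAP section 2.3:** SD 5 kg; within-participant correlation 0.9; target difference 0.75 kg; power 80%; 282 evaluable; 30% dropout; 448 randomised, 224 per level; 30% male; 40% racial/ethnic minority.

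**Assumed, because not stated:** two-sided alpha 0.05; a difference *d* in 6-month weight change of 0.5 to 2 kg, the same size for gender and for race/ethnicity; the two factors independent.

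**1. Reproducing the plan's sample size.** SD of change = 5 × √(2 × (1 − 0.9)) = 2.236 kg, a variance of 5 kg². Per level, n = 2 × (1.96 + 0.8416)² × 5 / 0.75² = 139.5, so 140, or 280 in total; with a t reference distribution, 282 gives power 0.801. Then 282 / 0.7 = 403, and 14 × 32 = 448. The plan's figures reproduce on a change SD of 2.24 kg and use no covariate adjustment.

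**2. Variance the two factors would carry.** A binary factor with prevalence p and difference *d* contributes p(1 − p)*d*². For both factors this is (0.3 × 0.7 + 0.4 × 0.6)*d*² = 0.45*d*².

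**3. Excess in the standard error.** With residual variance s², the ratio of the SE without the factors to the adjusted SE is f = √(1 + 0.45*d*² / s²).

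| *d* (both factors) | 0.45*d*² | f, s² = 5 (SD 2.24 kg) | f, s² = 25 (SD 5 kg) |
|---|---|---|---|
| 0.5 kg | 0.1125 | 1.011 | 1.002 |
| 1 kg | 0.45 | 1.044 | 1.009 |
| 2 kg | 1.80 | 1.166 | 1.035 |

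For race/ethnicity alone at s² = 5, f = √(1 + 0.24*d*² / 5) = 1.006, 1.024 and 1.092.

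**4. Consequence for the tests at s² = 5.** Completers per level: 448 × 0.7 / 2 ≈ 157. Adjusted SE = 2.236 × √(2/157) = 0.252 kg, so 0.75 / 0.252 = 2.97 and adjusted power = Φ(2.97 − 1.96) = 0.844. If allocation held both factors in balance, actual alpha = 2(1 − Φ(1.96f)) and power = Φ(2.97 − 1.96f):

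- 0.5 kg: alpha 0.047, power 0.839
- 1 kg: alpha 0.041, power 0.823
- 2 kg: alpha 0.022, power 0.754

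**5. Simulation.** 1,000 runs per scenario: 448 participants, 32 conditions, minimisation on both factors, 30% random dropout, and a constrained baseline and 6-month model with all factorial terms. Baseline weight was assumed to differ by 5 kg by gender and 2 kg by race/ethnicity.

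| *d* | Type I error, SAP model | Type I error, both factors with time interactions | Power, SAP model | Power, both factors with time interactions |
|---|---|---|---|---|
| 0 | 0.058 | 0.059 | 0.839 | 0.839 |
| 1 kg | 0.045 | 0.053 | 0.805 | 0.833 |
| 2 kg | 0.028 | 0.052 | 0.752 | 0.869 |

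The Monte Carlo error of a 5% rate is √(0.05 × 0.95 / 1000) = 0.7 points, so 0.058 and 0.059 are compatible with 0.05. The simulated SE ratio at 2 kg is 0.2995 / 0.2505 = 1.20, a little above the 1.17 from the formula. This is partly because the model conditions on baseline weight, which leaves a residual variance of 25 × (1 − 0.9²) = 4.75 rather than 5 kg².

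**The case against.** **The standard errors ignore the design.** A reader might infer this, and with it that the inference is invalid. The documents do not support it. Gender is in the model and accounts for gender differences in weight level. The error is conservative, the point estimates are not biased by the omission, and the 0.7 kg threshold works on point estimates. The effect on decisions runs through the significance clauses only.

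**The size is large.** This rests wholly on assumed inputs. Gaps of 2 kg on both factors at once are each more than 2.5 times the 0.75 kg target effect. An excess of 25% would follow only by taking 5 kg² as the total variance of change, √(5 / (5 − 1.8)) = 1.25, so that the two factors explain 1.8 / 5 = 36% of it. With 5 kg² as residual variance, the same gaps give 17%. At 1 kg the excess is about 4%.

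**The missing-data adjustment is invalid.** SAP section 4 does not say that covariates predicting missingness enter as main effects only; it leaves their form open. The likelihood also already uses each participant's observed weights. What stands is that the form should be stated, because a main effect alone would again be a constant shift.

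**The SAP is wrong about the factors.** It may not be. It writes of randomization in the past tense, and section 2.4 gives a data date of October 2019, whereas the protocol text is prospective. The SAP may record the allocation as run. If only gender was used, the race/ethnicity part falls away and the missing gender-by-visit term remains. That term may have been intended, but a programmer following the text would leave it out.

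**Conclusion.** The point holds as a specification defect with a conservative effect. The documents contradict each other on the balancing factors, and the gender term as listed does not adjust weight change. On the change SD that reproduces the plan's 282, the SE excess is about 1% to 17% for assumed differences of 0.5 to 2 kg on both factors, and power falls by about 1 to 9 points by formula (12 points between the two models in the simulation at 2 kg). If 5 kg is the SD of change, the excess is about 0.2% to 4%. It is nil if neither factor predicts change. These sizes assume two-sided alpha 0.05, dropout at random, and allocation that did balance both factors. The change is worth making because it is nearly free and makes the analysis match the allocation, not because the planned analysis would mislead.

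**What to change.** 1. Confirm from the allocation program which factors and which method were used. Then reconcile the two protocol descriptions with the parenthesis in SAP section 4; do not correct the parenthesis before that check.
2. In SAP section 4, enter each factor actually used together with its interaction with visit: gender and gender-by-visit in any case, and race/ethnicity and race/ethnicity-by-visit if it was used, in the categories the algorithm used.
3. In the missing-data paragraph of the same section, state that any covariate added because it predicts missingness also enters with its visit interaction.

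Cost: a few sentences and a few extra model terms. Both variables are already collected at baseline, and the sample size does not change.

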## 5 Table shells and proposed figures

Potential format of table 1 (from Piper et al.):

**Table 1** Demographic and smoking history characteristics.

	Total sample	Preparation gum		Preparation patch		Preparation counseling		In-person counseling		Phone counseling		Medication duration	
		On	Off	On	Off	On	Off	On	Off	On	Off	On	Off
Women (%)	54.6	54.3	55.0	55.3	53.9	54.6	54.7	55.4	53.9	53.8	55.5	56.3	53.2
Age (mean, SD)	45.8 (12.0)	45.3 (11.9)	46.2 (12.2)	45.2 (11.8)	46.3 (12.3)	46.2 (12.2)	45.3 (11.9)	45.8 (12.2)	45.7 (11.9)	45.1 (12.0)	46.4 (12.0)	45.1 (12.2)	46.4 (11.6)
High School diploma or GED only (%)	31.4	32.0	30.7	31.4	31.5	34.5	28.4	30.1	32.7	32.5	30.4	30.6	32.2
At least some college (%)	58.7	57.2	60.2	57.6	59.7	55.7	61.5	58.7	58.2	58.1	59.1	60.1	57.3
White (%)	87.8	87.8	87.8	87.8	87.7	88.5	87.0	87.8	87.7	89.5	86.0	87.0	88.4
African American (%)	7.8	9.0	6.5	8.6	7.0	6.7	8.9	8.4	7.2	7.0	8.6	9.3	6.4
Hispanic (%)	3.9	4.5	3.1	3.1	4.7	4.2	3.5	4.2	3.5	4.5	3.2	5.1	2.8
Health system A (%)	57.3	55.5	59.4	59.9	54.5	56.8	57.8	61.1	53.6	59.1	55.5	60.9	54.1
Cigs/day (mean, SD)	17.7 (8.2)	17.5 (8.4)	17.9 (7.9)	18.1 (8.0)	17.2 (8.4)	17.8 (8.4)	17.5 (8.1)	17.9 (8.2)	17.4 (8.2)	18.1 (8.4)	17.3 (7.9)	17.8 (7.8)	17.6 (8.5)
Baseline carbon monoxide (mean, SD)	20.3 (11.4)	20.3 (11.7)	20.4 (11.0)	20.6 (10.7)	20.0 (12.1)	20.6 (11.3)	20.0 (11.4)	20.3 (11.6)	20.4 (11.1)	20.2 (11.4)	20.4 (11.3)	19.6 (10.8)	21.0 (11.9)
FTND (mean, SD)	4.8 (2.2)	4.8 (2.1)	4.8 (2.3)	4.9 (2.2)	4.7 (2.1)	4.9 (2.2)	4.7 (2.1)	4.9 (2.1)	4.7 (2.1)	4.9 (2.2)	4.8 (2.1)	4.8 (2.2)	4.8 (2.1)
Heaviness of Smoking Index (mean, SD)	3.1 (1.4)	3.1 (1.4)	3.1 (1.4)	3.2 (1.4)	3.0 (1.4)	3.1 (1.5)	3.0 (1.4)	3.2 (1.4)	3.0 (1.5)	3.2 (1.4)	3.0 (1.4)	3.1 (1.4)	3.1 (1.4)

On = factor was present or at the intensive level or longest duration (e.g. intensive counseling, 16 weeks of medication). Off = factor was not present or was at the minimal level or shortest duration (e.g. minimal counseling, 8 weeks of medication). The study was conducted in two healthcare systems (A and B). FTND = Fagerström Test of Nicotine Dependence; SD = standard deviation; GED = general educational development.

[figure not shown]
**Table 2.** Potential format of regression results table (from Piper et al.)

**Table 3** Logistic regression models for 2-, 16- and 26-week point-prevalence outcome.

Variable	2 weeks post-TQD				16 weeks post-TQD				26 weeks post-TQD			
	Unadjusted		Adjusted a		Unadjusted		Adjusted a		Unadjusted		Adjusted a	
	b	P-value	b	P-value	b	P-value	b	P-value	b	p-value	b	P-value
Intercept	-0.26	0.001	0.43	0.45	-0.70	< 0.001	-0.69	0.25	-1.04	< 0.001	-0.34	0.59
Preparation patch	0.01	0.87	0.04	0.66	0.08	0.34	0.11	0.22	0.09	0.34	0.11	0.24
Preparation gum	-0.01	0.95	-0.00	0.96	0.11	0.21	0.12	0.19	0.12	0.20	0.12	0.23
Preparation counseling	0.03	0.69	0.04	0.60	0.18	0.04	0.19	0.03	0.11	0.23	0.11	0.23
Cessation in-person counseling	0.14	0.10	0.15	0.07	0.05	0.54	0.06	0.48	-0.04	0.68	-0.03	0.80
Cessation phone counseling	-0.03	0.72	-0.03	0.75	0.05	0.59	0.06	0.54	0.12	0.21	0.12	0.20
Medication duration	0.02	0.78	0.01	0.91	0.08	0.39	0.07	0.46	-0.02	0.80	-0.03	0.73
Preparation patch × preparation gum	0.05	0.56	0.05	0.54	0.04	0.68	0.04	0.65	0.06	0.54	0.06	0.53
Preparation patch × preparation counseling	0.16	0.050	0.18	0.04	0.15	0.10	0.17	0.07	0.18	0.07	0.19	0.06
Preparation patch × cessation in-person	0.14	0.09	0.15	0.08	0.19	0.03	0.20	0.03	0.22	0.02	0.22	0.02

Another example of showing effects:

